15.2.3 Other Significant Adverse Events

The frequency (number and percentage) of participants with each of the following will be presented for treatment-emergent irAEs, by treatment group:

- The overall summary of irAEs table will include the following categories:
 - All irAEs
 - Serious irAEs
 - irAEs, NCI-CTCAE [version 5.0]) \geq Grade 3
 - irAEs leading to permanent treatment discontinuation
 - irAEs leading to death

The listing of all irAEs will also be provided with the relevant information with a flag for irAEs with onset outside of the on-treatment period. In case of irAEs percentage is more than 10% of events a summary by SOC and PT will be presented. In case of any irAE leading to death a separate summary by SOC and PT will be included.

The frequency (number and percentage) of participants with each of the following will be presented for treatment-emergent IRR, by treatment group:

- The overall summary of IRR table will include the following categories:
 - All IRR
 - Serious IRR
 - IRR, NCI-CTCAE [version 5.0]) \geq Grade 3
 - IRR leading to permanent treatment discontinuation
 - IRR leading to death

In case of IRR percentage is more than 10% of events a summary by SOC and PT will be presented. In case of any IRR leading to death a separate summary by SOC and PT will be included.

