Importantly, these clinical trials demonstrated that increased efficacy offered by these treatments was paralleled by acceptable safety profile. Treatment-related adverse events (TRAEs)  $\geq$  Grade 3 occurred in 46% of patients treated with Nivolumab plus Ipilimumab, 62.9% of patients treated with Pembrolizumab plus Axitinib and in 56.7% of patients treated with Avelumab plus Axitinib compared to 55.4% to 63.0% of patients receiving Sunitinib. TRAEs  $\geq$  Grade 3 occurred in  $\geq 10\%$  of patients were increased lipase levels among patients receiving Nivolumab plus Ipilimumab (10.0%), hypertension, and increased alanine aminotransferase levels in patients treated with Pembrolizumab plus Axitinib (22.1% and 13.3%, respectively), and hypertension in patients treated with Avelumab plus Axitinib (25.6%). Death due to toxicity of trial treatment was documented in 1.5% of patients treated with Nivolumab plus Ipilimumab, 0.9% of patients receiving Pembrolizumab plus Axitinib and 0.7% of patients treated with Avelumab plus Axitinib. About 22%, 10.7%, and 7.6% of patients treated with Nivolumab plus Ipilimumab, Pembrolizumab plus Axitinib, and Avelumab plus Axitinib, respectively, discontinued both study drugs due to TRAEs ([Rini 2019b](#)).

Furthermore, therapy modifications were frequent across the studies. For instance, delays in administration of Nivolumab and Ipilimumab occurred in 58% and 27% of patients, respectively ([Motzer 2018](#)), while 69.9% of patients had interruption of either Pembrolizumab or Axitinib ([Rini 2019a](#)). Axitinib dose was reduced in 20.3% of patients co-treated with Pembrolizumab and in 42.2% of patients co-treated with Avelumab ([Rini 2019a, Motzer 2019](#)). High doses of glucocorticoids for management of immune-related adverse events (AEs) were required by 35% of patients on Nivolumab plus Ipilimumab and only by 11.1% of patients on Avelumab plus Axitinib therapy ([Motzer 2018, Motzer 2019](#)). Among patients treated with Avelumab plus Axitinib, 38.2% had any grade pre-specified immune-related AEs, which were most frequently immune-related thyroid disorders (24.7% of patients) ([Motzer 2019](#)). In 9.0% of patients, these immune-related AEs were of  $\geq$  Grade 3 ([Motzer 2019](#)).

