Safety of Avelumab plus Axitinib was also investigated in an open-label, dose-finding phase 1b study JAVELIN Renal 100 (NCT02493751). About 58% of enrolled treatment-naïve advanced RCC patients experienced  $\geq$  Grade 3 TRAEs, which were most frequently hypertension (29.0%) and increased concentrations of alanine aminotransferase, amylase, and lipase, and palmar-plantar erythrodysesthesia syndrome in 7.0% of patients each. About 2.0% of patients died due to treatment-related autoimmune myocarditis ([Choueiri 2018](#)).

In general, the safety profile of combined Avelumab plus Axitinib therapy is in line with that of single agents. Recently, phase 1 JAVELIN Solid Tumor study (NCT01772004) provided further safety data for first-line Avelumab monotherapy in metastatic RCC. In this study, 12.9% of

patients had a  $\geq$  Grade 3 TRAE, which was most frequently increased lipase levels ([Vaishampayan 2019](#)). About 3.2% of patients had serious TRAEs (colitis and hyperthermia). TRAEs led to drug discontinuation in 4.8% of patients (anaphylactic reaction, aspartate aminotransferase increase, and nephritis). Infusion-related reactions occurred in 35.5% of patients and 29.0% had immune-related AEs with thyroid disorders and immune-related rash documented in  $\geq 10.0\%$  of patients. Axitinib was compared against Sorafenib in phase III study in previously untreated metastatic RCC patients. Most frequent all-cause AEs  $\geq$  Grade 3 in Axitinib arm were hypertension, asthenia, diarrhea, weight decrease, palmar-plantar erythrodysesthesia, and fatigue ([Hutson 2013](#)). About 5.0% of patients had serious TRAEs, including diarrhea, atrial flutter, cardiac arrest, myocardial infarction, gastric ulcer, gastrointestinal hemorrhage, melena, nausea, rectal hemorrhage, vomiting, retroperitoneal hematoma, asthenia, mucosal inflammation, dehydration, decreased appetite, aortoduodenal fistula, and hypertensive crisis. Compared to other VEGF receptor inhibitors, Axitinib causes less hepatic and hematologic toxicity and thus, it is considered a better partner for combined treatments with other anti-cancer agents such as Avelumab.

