To analyze the nature, severity, duration, frequency, and timing of Adverse Events (AEs) that occurred from the index date up to 90 days post discontinuation of Avelumab plus Axitinib or completion of the 24 months (ie, end of the study) follow-up from the index date, whichever occurs first	Endpoint: Frequency and nature of all-cause AEs according to Medical Dictionary for Regulatory Activities (MedDRA) system organ class (SOC) and preferred term (PT) that occurred from the index date up to 90 days post discontinuation of Avelumab plus Axitinib or completion of the 24 months (ie, end of the study) follow-up from the index date, whichever occurs first.	15.1.1
To assess time to therapy discontinuation due to AE \geq Grade 3	Endpoint: Duration of Avelumab plus Axitinib therapy among patients who discontinued the study drugs due to all-cause AEs \geq Grade 3.	15.1.2
To assess therapy modifications due to AE related to Avelumab plus Axitinib therapy and management of AE related to Avelumab plus Axitinib therapy	Endpoint: Percentage of patients with therapy modifications due to AE related to Avelumab plus Axitinib therapy (eg, therapy interruptions and reductions of infusion rate for Avelumab, therapy interruptions, and dose reductions for Axitinib).	15.1
To determine percentage of patients receiving later-line therapy and frequency distribution of later-line therapy regimes among patients progressing on Avelumab plus Axitinib	Endpoint: Percentage of patients receiving later-line therapy and frequency distribution of later-line therapy regimes among patients progressing on Avelumab plus Axitinib including the names of medications of monotherapy/combination treatment used in second-line and third-line therapy.	15.1
To assess time to second-line therapy initiation (T2LT)	Endpoint: Time interval from Avelumab plus Axitinib therapy discontinuation to the initiation of second-line therapy.	14.2
To assess patient-reported potential signs and symptoms of immune-related AEs	Endpoint: Frequency of patient-reported signs and symptoms of potential immune-related AEs. Immune-related AEs may include immune-mediated pneumonitis, immune-mediated colitis, immune-mediated hepatitis, immune-mediated endocrinopathies, immune-mediated nephritis with renal dysfunction.	15.2.3

6 Overview of Planned Analyses

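### SAP 15.2.3 makes the SOC/PT tables of immune-related events and infusion reactions depend on an undefined share of events, so they can be dropped even when over a third of patients are affected; the gap is clearest for infusion reactions

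*SAP*

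**What the plan says.** SAP 15.2.3 sets the unit of its irAE table at the outset: "The frequency (number and percentage) of participants with each of the following will be presented for treatment-emergent irAEs, by treatment group". The table has five rows: all, serious, Grade 3 or higher, leading to permanent discontinuation, and leading to death. The IRR table has the same layout. Neither shows the type of event. Type appears only in a further table, which is conditional for irAEs ("In case of irAEs percentage is more than 10% of events a summary by SOC and PT will be presented") and for IRRs ("In case of IRR percentage is more than 10% of events a summary by SOC and PT will be presented"). Fatal irAEs or IRRs get an SOC/PT summary in any case. A listing of every irAE is promised; 15.2.3 promises none for IRRs.

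SAP 15.1 defines the two groups. An irAE is an event ticked as immune-related on the eCRF. An IRR is either a hypersensitivity-type term starting on the infusion day or the day after, or one of nine signs and symptoms (pyrexia, dyspnea and back pain among them) that starts on the infusion day and resolves by the next day. SAP 15.1 also sets a default for its summaries: participants, by SOC and PT.

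SAP 5 assigns the immune-related objective to 15.2.3 and gives examples of type: "Immune-related AEs may include immune-mediated pneumonitis, immune-mediated colitis, immune-mediated hepatitis".

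The only background rates are in Protocol 7 and are per patient. For the combination: "Among patients treated with Avelumab plus Axitinib, 38.2% had any grade pre-specified immune-related AEs". For avelumab alone: "Infusion-related reactions occurred in 35.5% of patients and 29.0% had immune-related AEs with thyroid disorders".

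**The concern.** The tables count participants, but the condition that decides whether the breakdown exists counts events, and the SAP does not say which events (all AEs or only treatment-emergent ones). Two programmers could reach opposite decisions from the same data.

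An event share also measures the wrong thing. It falls when sites record more unrelated AEs, even if immune or infusion toxicity is unchanged. Whether a safety table is produced would then depend on how much other AE reporting there is.

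At stake is whether the report shows which irAEs and IRRs occurred, with frequencies, or only how many patients had any. The general TEAE tables cannot fully replace the breakdown. They pool flagged and unflagged events under the same PT, and for IRRs they cannot separate a back pain that began on the infusion day from any other back pain.

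**Working it through.** The plan gives no probability of meeting the trigger and no event counts, so there is no stated figure to reproduce. The check compares the two possible readings.

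**Inputs from the documents**
- irAE rate p = 0.382 of patients on the combination (Protocol 7).
- IRR rate p = 0.355 of patients on avelumab monotherapy (Protocol 7).
- About 100 patients (Protocol 9.5).
- Threshold 10% (SAP 15.2.3).

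**Inputs assumed, because the documents do not give them**
- k, events per affected patient: 1 to 3.
- m, AEs of any kind per patient: varied. If the denominator is treatment-emergent events, only AEs within the on-treatment period of SAP 9.8 count towards m.

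**Participant reading.** The trigger is met if at least 11 of 100 patients are affected. The exact binomial probability is about 1.000 at 38.2% and at 35.5%. With the rates halved, it is 0.99 for irAEs (19.1%) and 0.98 for IRRs (17.75%).

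**Event reading.** Expected share = p × k / m. This exceeds 0.10 only if m < p × k / 0.10. For irAEs with k = 1 the break-even is 0.382 / 0.10 = 3.82; for IRRs it is 0.355 / 0.10 = 3.55.

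| k | Break-even m, irAEs | Break-even m, IRRs |
|---|---|---|
| 1 | 3.8 | 3.6 |
| 1.5 | 5.7 | 5.3 |
| 2 | 7.6 | 7.1 |
| 3 | 11.5 | 10.7 |

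Above the break-even the trigger is missed on average; below it, it is met. For irAEs with k = 1 the expected share is 0.382 / 3 = 12.7% at m = 3, 7.6% at m = 5 and 3.8% at m = 10. With k = 2 it is 0.764 / 5 = 15.3% at m = 5 and 7.6% at m = 10.

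**Chance of meeting the trigger on the event reading.** This comes from a simulation of 100 patients. The number affected is binomial, and other AEs are overdispersed counts with the mean set so that all AEs average m.

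| Group, k | Smallest m | Middle m | Largest m |
|---|---|---|---|
| irAE, k = 1 | 0.95 (m = 3) | 0.37 (m = 4) | 0.03 (m = 5) |
| irAE, k = 2 | 0.99 (m = 5) | 0.37 (m = 8) | 0.04 (m = 10) |
| IRR, k = 1 | 0.86 (m = 3) | 0.21 (m = 4) | 0.01 (m = 5) |
| IRR, k = 2 | 0.97 (m = 5) | 0.23 (m = 8) | 0.01 (m = 10) |

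Within each row the irAE or IRR rate is fixed and only the total AE count changes, yet the table goes from near-certain to near-impossible.

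**Lower IRR rate.** Patients enter after 1 or 2 cycles (Protocol 9.2.1), so the IRR rate from the index date may differ from 35.5%. If it were half, the k = 1 break-even would be 0.1775 / 0.10 = 1.8 AEs per patient.

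**The case against.** The strongest reply is that the trigger is meant to count participants. It follows a table whose only percentages are of participants, and SAP 9 bases proportions on participants unless otherwise stated. On that reading the tables would almost certainly appear at the cited rates. This is a fair guess at the intent, but the sentence says events, and SAP 9 gives way to a stated exception. The text does not settle it.

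A second reply is that irAEs are covered elsewhere, and much of this stands. The irAE listing is unconditional. SAP 15.1.1 plans a summary of immune-related signs and symptoms with no threshold, and the SAP 15.1 default would make it participant-based and by SOC and PT. The tables of drug-related TEAEs narrow the mixing further, though they do not isolate irAEs. The immune-related endpoint in SAP 5 concerns patient-reported signs and symptoms, and the types it names are examples, so it does not itself require an irAE table by PT.

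This cover does not extend equally to IRRs. Their PTs appear in the general tables and in the all-AE listings, but nothing there is said to mark an event as an IRR; only the death listing is stated to carry an irAE or IRR flag. On the other hand, Protocol 9.7.3 lists no IRR table, so the protocol's own list does not promise this breakdown.

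A reader might infer more: that at the documents' own rates the trigger would usually be missed, and that the breakdown of both risks would be suppressed. The documents do not support that. Their rates are per patient and far above 10%. A miss needs assumed values of k and m, and the result flips within the range tried. The 38.2% refers to pre-specified irAEs in a trial, while here the irAE is an investigator's tick; the 35.5% is from monotherapy.

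**Conclusion.** The condition is a real defect of specification. Its denominator is undefined, it does not match the participant-based tables around it, and read literally it depends on background AE reporting. On the literal reading the trigger can be missed with more than a third of patients affected: at one event per affected patient, above about 3.8 AEs per patient for irAEs and about 3.6 for IRRs. These break-evens rest on the cited rates and the assumed k, and rise in proportion to k. Whether patients in this study will exceed them cannot be told from the documents.

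The consequence is limited to the dedicated aggregate tables of non-fatal events. For irAEs the loss would be partial, given the listing and the 15.1.1 summary. For IRRs it would be clearer, because those identified by timing cannot be recovered from the general TEAE tables and 15.2.3 gives them no listing. The point is modest in a descriptive single-arm study, but worth correcting because the change is so small.

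**What to change.** Delete both 10% conditions in SAP 15.2.3. State that treatment-emergent irAEs and IRRs are always presented by SOC and PT, any grade and Grade 3 or higher, as number and percentage of participants in the analysis set.

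If a threshold is kept for layout, define it as a percentage of participants in the analysis set. Deletion is the safer choice for IRRs: if their true rate here were 10% or 15%, a participant threshold with 100 patients would be met with probability 0.42 or 0.90 (binomial, at least 11 affected).

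The cost is SAP wording and a few short tables. The irAE flag is already on the eCRF and the IRR derivation is already specified in SAP 15.1, so no new data are needed.

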15.3 Clinical Laboratory Evaluation

Not applicable.

15.4 Vital Signs

Vital signs including systolic blood pressure, diastolic blood pressure and pulse will be collected upon availability at baseline only (see [Section 11.1](#)) while body weight will be collected upon availability all over the study. Weight at Baseline will be summarized as described in [Section 11.1](#) while weight collected after Baseline visit will only be listed along with demographic data.

15.5 Other Safety or Tolerability Evaluations

Physical Examinations will be collected upon availability at Baseline visit and will only be listed.

16 Analyses of Other Endpoints

16.1 Pharmacokinetics

Not applicable.

16.2 Pharmacodynamics

Not applicable.

16.3 Patient-Reported Outcome

The NCCN-FACT Fksi-19 scores (total and subscales described in [Section 9.10](#)) of the HRQoL at the index date and at every 6 weeks will be summarized using descriptive statistics for continuous variables.

Possible trend in HRQoL will be analyzed by repeated measure analysis. The repeated measure model will be handled with mixed effects models using PROC MIXED with an unstructured correlation matrix to model the within-patient errors, unless the model does not converge, in which case the heterogeneous Toeplitz covariance structure followed by the heterogeneous first-order autoregressive covariance structure will be checked. Parameters will be estimated using the Newton-Raphson algorithm. Denominator degrees of freedom will be estimated using the Kenward-Roger approximation by fitting values from post-baseline scheduled visits. This likelihood-based approach is tolerant of missing data if they are Missing at Random (MAR).

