### **Patient-reported outcomes:**

- HRQoL using the NCCN-FACT FKSI-19 at the index date and at every third cycle of Avelumab treatment (intervals of about 6 weeks) thereafter until the end of treatment or end of 24 months of study follow-up, whichever occurs first
  - The NCCN-FACT FKSI-19 is a 19-item self-reported questionnaire that captures symptom severity and interference in activity and general health perceptions ([Rothrock 2013](#), [Rao 2009](#))
  - The NCCN-FACT FKSI-19 covers 4 subscales of the FKSI:
    1. DRS-P, disease-related symptoms subscale—physical
    2. DRS-E, disease-related symptoms subscale—emotional
    3. TSE, treatment side effects subscale
    4. Functional and well-being (FWB), function and well-being subscale ([Rao 2009](#))
  - Each of the items is scored on a five-point scale from zero (not at all) to 4 (very much).

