9.2 Definition of baseline and change from baseline

Baseline is defined as the non-missing assessment reported at index date (Baseline visit).

Absolute and percent changes from baseline are defined as

$$\text{absolute change} = \text{visit value} - \text{baseline value}$$

$$\text{percent change} = 100 * (\text{visit value} - \text{baseline value}) / \text{baseline value}$$

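### The HRQoL repeated-measures model is fitted to post-baseline forms only and its response, fixed effects and contrast are not stated, so no modelled change from the index date is defined

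*SAP*

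**What the plan says.** The protocol lists the patient-reported outcome as "HRQoL using the NCCN-FACT FKSI-19 at the index date and at every third cycle of Avelumab treatment", continuing until end of treatment or 24 months, whichever is earlier (Section 9.1.2.2). SAP 9.2 takes the index-date assessment as baseline and defines absolute and percent change from it.

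SAP 16.3 plans two analyses. The first is descriptive: "HRQoL at the index date and at every 6 weeks will be summarized using descriptive statistics for continuous variables". The second is modelled: "Possible trend in HRQoL will be analyzed by repeated measure analysis". The model is described as "mixed effects models using PROC MIXED with an unstructured correlation matrix to model the within-patient errors", with heterogeneous Toeplitz and then heterogeneous first-order autoregressive structures as fallbacks. Two sentences decide this point: "Denominator degrees of freedom will be estimated using the Kenward-Roger approximation by fitting values from post-baseline scheduled visits", and then "This likelihood-based approach is tolerant of missing data if they are Missing at Random (MAR".

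SAP 16.3 does not say whether the response is the score or its change, which fixed effects enter, what part the index-date score plays, or which contrast measures the trend.

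**The concern.** The data rule in SAP 16.3 sits in the sentence on degrees of freedom, but those degrees of freedom come from the same fit, so it is natural to read it as defining the data modelled. Three things follow.

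- With the score as response, the trend runs from Week 6 onward. The first step, index date to Week 6, lies outside the model, and no modelled change from index is specified.
- A patient without an in-window post-baseline form adds nothing. SAP 9.7 makes this more likely: the Week 6 window covers days 29 to 56, the next opens on day 70, and out-of-window forms are only listed.
- A likelihood fit protects against dropout that depends on observed values in the model. Collection stops at end of treatment, so missingness follows discontinuation. If discontinuation is related to the index score, the variable that would make missing at random plausible is not among the fitted responses.

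What is at stake is the only modelled HRQoL result in a single-arm study, where no comparator could expose a drift caused by who stays on treatment.

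**Working it through.** The documents give no power, effect size, SD, correlation or dropout figure for HRQoL, so there is no figure of the plan's to reproduce. The check is a simulation on assumed inputs.

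**Inputs from the documents.** About 100 patients (Protocol 9.5); total score 0 to 76, higher is better (SAP 9.10); forms every 6 weeks (SAP 9.7); response vector restricted to post-baseline visits (SAP 16.3).

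**Assumed inputs.** Normal scores with SD 10; correlation 0.5 or 0.7 exchangeable, or AR(1) 0.8; visits at Weeks 6, 12, 18 and 24; true change zero. Dropout before each visit follows logit(p) = -2.2 - g·z, where z is the standardised score. At z = 0 this gives p = 1/(1 + exp(2.2)) = 0.10. With g = 0.5 or 0.8, the odds of leaving rise by exp(0.5) = 1.65 or exp(0.8) = 2.23 per SD worse score.

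**Method.** For monotone dropout, the maximum-likelihood visit means under an unstructured covariance follow from regressing each visit on the earlier ones in sequence. They were computed once from post-baseline scores alone and once with the index score as first response, on 400,000 simulated patients per setting so that sampling noise is negligible.

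| Setting (true change zero) | Post-baseline-only fit: Week 24 mean minus index mean | Post-baseline-only fit: Week 6 to 24 trend | Index score in response: Week 24 minus index |
|---|---|---|---|
| Worse index score leaves, exchangeable 0.5 to 0.7 | +0.5 to +1.0 | +0.2 to +0.4 | 0.0 |
| Dropout follows latest score, exchangeable | smaller, still above 0 | 0.0 | 0.0 |
| Worse index score leaves, AR(1) 0.8 | smaller, still above 0 | about -0.35 at g = 0.8 | 0.0 |
| Dropout unrelated to score | 0.0 | 0.0 | 0.0 |

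The AR(1) sign has a simple cause. Losing low index scorers before Week 6 lifts the fitted mean in proportion to the correlation with the index score. That correlation is 0.8 at Week 6 and 0.8^4 = 0.41 at Week 24, so the lift fades and looks like a decline.

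For scale, in 3,000 simulated studies of 100 patients the SD of the estimated Week 24 change was 0.92 to 1.27. A shift of 0.5 to 1.0 is thus roughly half to one standard error.

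**Wider settings.** With six post-baseline visits, 0 to 20% lost before the first form, 12% lost per later visit and g from 0.7 to 1.0:

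- Exchangeable 0.5 to 0.7, dropout driven by the index score: last visit +0.5 to +2.0 against index; trend +0.4 to +0.8.
- AR(1) 0.8: last visit 0.0 to +0.6; trend 0.0 to -1.1.
- Better-scoring patients leaving instead: signs reverse, with -1.4 at the last visit and -0.6 in the trend in the setting run.
- Index score in the response vector: true change recovered within about 0.05 point, whether the truth was 0 or -3.

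**The unstated response matters.** At 10% early loss in the same settings, modelling change from index without a covariate gives -0.6 to -2.7, a bias towards worsening. With the score as response, the Week 24 shift above is upward. Both choices are compatible with the text of SAP 16.3.

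**The case against.** The strongest reply is that this is missing detail in a minor analysis. SAP 16.3 lists no fixed effects at all, not even time, so its silence cannot show that the index score is excluded. A change-from-index response, or an index covariate, would fit the sentence about post-baseline visits, and SAP 9.2 supplies the definition ("Absolute and percent changes from baseline are defined as"). Protocol 9.7 plans descriptive change from baseline for observed cases, and the objective asks for HRQoL at the index date and later, not for a modelled change. All analyses are descriptive. The index date itself comes after one or two cycles, so change from it is not change from a pre-treatment value.

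Much of this stands, and it rules out three stronger readings that a reader might infer.

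- *That the SAP bars the index score from the model.* It excludes it as a response; on covariates it is silent.
- *That the result will drift towards improvement.* The documents say nothing on which patients leave or how scores correlate, and the trend bias can be positive, nil or negative.
- *That the HRQoL objective goes unanswered.* Index and later scores are summarised descriptively.

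What does not stand is that only detail is missing. A rule on which values are fitted is stated, and it leaves out an observation already collected on the same scale. Nor do the descriptive summaries stand in for the model: in the wider settings with worse-scoring patients leaving, the raw mean of forms still arriving at the last visit was +1.0 to +4.6 points above the index mean, further off than the post-baseline-only fit.

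**Conclusion.** The point holds as a gap in specification with a clear and nearly free improvement. As written, the model starts at Week 6, defines no change from index, uses nothing from patients with only an index-date form, and makes a missing-at-random statement that does not extend to dropout depending on the index score. The possible distortion is modest: at most about one point at Week 24 and 0.4 point in the Week 6 to 24 trend under the main assumptions, larger with more visits and more early loss. Size and sign both rest on the assumed SD, correlation and dropout pattern. The benefit of including the index score is steadier: it removed the bias in every setting where dropout depended on scores already observed. It would not do so if dropout depended on scores never recorded.

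**What to change.** Rewrite the model paragraph in SAP 16.3 as follows.

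- The response vector is the FKSI-19 score with the index-date score as first time point. Visit (index date, Week 6, Week 12 and so on) is a categorical fixed effect.
- Report the least-squares mean change, visit minus index, with model-based 95% CIs, and one trend contrast fixed in advance.
- Label the result as on-treatment, since forms stop at end of treatment.
- Report how many patients have no in-window post-baseline form.

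Modelling change from index with the index score as covariate is not a substitute. Patients without a post-baseline form still drop out, and a post-baseline fit with the index score as covariate, evaluated at the mean index score of the modelled patients, left -0.25 to -0.88 point at 10% early loss.

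The cost is SAP wording and a few lines of code, with no new data. An unstructured matrix grows from 18 × 19/2 = 171 to 19 × 20/2 = 190 parameters. With about 100 patients, the fallback structures already in SAP 16.3 are likely to be needed either way.
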